- 2) Subjects with known cystic kidney disease or posterior ureteral valves (subjects with solitary kidney, single multicystic/dysplastic kidney, hydronephrosis will not be excluded if renal function is preserved)
- 3) Subjects with known metabolic disorder
- 4) Premature infants born < 30 weeks gestation and < 30 days old due to risk of intraventricular hemorrhage

Subjects in severe cardiogenic shock post-operative requiring extra-corporeal membrane oxygenation (ECMO) or left ventricular assist device (LVAD) will be withdrawn from the study.

IV. Randomization and Blinding

Subjects will be randomized to the treatment group or control group in a 1:1 ratio to receive sodium bicarbonate (treatment group) or placebo (control group). Allocation will be based on random, computer-generated numbers in permuted blocks of 10. Study drug and placebo will be prepared and dispensed by the pharmacy according to randomization. The treatment will be administered in an identical fashion to subjects in both arms. The investigators involved in the study, clinicians and study subjects will be blinded to the treatment assignment.

V. Study Procedures

The outline of study procedures is as follows:

| Study Procedures | | | | | | | | | | | |
|-------------------------------------|-----------|---------------|--|-----------------|------|------|-------|-------|-------|---------|---|
| | Screening | Pre-Operative | | Intra-Operative | 2 hr | 4 hr | 12 hr | 24 hr | 48 hr | 30 days | |
| Review Inclusion/Exclusion Criteria | x | | I N T E R V E N T I O N | | | | | | | | |
| Informed Consent/Assent | x | | | | | | | | | | |
| Randomization | | x | | | | | | | | | |
| Demographics/Medical History | x | | | | | | | | | | |
| Height and Weight | x | x | | | | | | | | | x |
| Serum creatinine/BUN | x | x | | | | x | x | x | x | x | x |
| Serum electrolytes | x | x | | | x* | x | x | x | x | x | x |
| Urine pH | | x | | | x* | x | x | x | x | x | |
| CBC with differential | x | x | | | | | | | | | |
| Serum NGAL | | x | | | | x | x | x | x | x | |
| Serum pH | | x | | | x* | x | x | x | x | x | |
| Urine Output Monitoring | | x | | | x | x | x | x | x | x | |

* Serum and urine pH and serum electrolytes will be done at the discretion of anesthesia and bypass team as per protocol.

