Items marked in **RED** indicate procedures being done specifically for the research study. Blood draws at 4 hours post-operatively are standard practice for certain patients, based on complexity of the surgical procedure, and will be done for

research purposes on some patients who had less complex surgeries. All other procedures represent standard practice for all patients undergoing cardiopulmonary bypass for correction of congenital heart lesions.

a. Screening Visit

Eligibility and demographic data will be collected on all children scheduled for cardiac surgery with cardiopulmonary bypass during the study interval. Subject and disease characteristics will be recorded for all ineligible subjects and those declining participation. Potential subjects will be screened using the protocol inclusion and exclusion criteria. Pre-surgical testing laboratory data, collected as part of standard care, will be reviewed. Study subjects who meet the eligibility criteria will be asked to participate in the study in person by physicians known to them in clinic or in the hospital. Parental/guardian permission (informed consent) and, if applicable, child assent, will be obtained prior to any study related procedures being performed.

b. Perioperative Management

As part of their standard care, subjects will have baseline height, weight, comprehensive metabolic panel, complete blood count and serum pH done on the day of surgery at the time of IV and arterial line insertion. Subjects will then be randomized into one of the treatment groups and will receive the intervention at the start of surgery.

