Treatment Arm: Patients randomized to the intervention of receiving NaHCO₃ perioperatively will initially receive the current standard anesthetic and perfusion approach at CCMC, which includes a cardiopulmonary pump priming solution containing 0.2mEq per milliliter of crystalloid. At the start of the surgery, the patient will begin to receive NaHCO₃ as a continuous infusion of D5% 1/3NS + 100 meq/L NaHCO₃ + 20 meq/L KCl at maintenance IVF (solution contains ~154 meq of sodium which is equivalent to normal saline). The strength of NaHCO₃ is based on a dose of 150 meq/m²/day (reference range 120-200mEq/m²/day [Lexicomp, 18th Ed., 2011-12]) and IVF maintenance of 1500 ml/m²/day. While the patient is undergoing CPB, calculated base deficits more negative than -3 will be corrected by giving NaHCO₃ according to the formula: base deficit * patient weight in kilograms/ 3. Tromethamine (THAM) may be used in the neonatal population while undergoing CPB if the serum sodium levels have increased to greater than 145 mEq/dL. Blood gas serum sodium, potassium and calcium will be monitored during the surgery and corrections will be made by the anesthesiologist. The NaHCO₃ infusion will continue for the first 24 hours after the discontinuation of CPB (based on current data from CCMC PICU: 85% of patients who develop AKI do so in the first 24 hours, and duration of AKI is <48 hours in 75% patients (reference Aydin, Annals of Thoracic Surgery, 2012). After 24 hours of receiving the NaHCO₃ infusion, the IVF administered to the patient will be the standard solutions used in the PICU at CCMC, notably a sodium concentration with dextrose along the spectrum of D5 0.33% NaCl through D5 0.45% NaCl, depending on the patient's serum electrolyte profile.

Control Arm: At the start of surgery, patients in the control arm will receive D5% Normal Saline + 20 meq/L KCL at maintenance IVF. The standard approach to perfusion for CPB, including the pump prime solution containing NaHCO₃ as well as replacement of NaHCO₃ for calculated base deficits will be administered as described above. After 24 hours, standard IVF, not containing NaHCO₃ or Na acetate will be administered for

the duration of the PICU stay as required, determined by the clinicians primarily caring for the patient postoperatively.

d. Hospital Course

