Serum creatinine, NGAL and urine pH will be monitored at 2, 4, 12, 24, and 48 hours. Urine pH will be collected and tested by a research nurse from the division of pediatric nephrology according to the study outline (see section V.). The research nurse will be blinded to whether the patients being evaluated are enrolled in the control or intervention arms. Data regarding patient urine pH will be identified by study-specific patient number, and stored in a password-protected electronic spreadsheet on the computer of the research nurse. Investigators will be blinded to the results of the urine pH, maintaining the double-blinded study design. Urinary output will be targeted to maintain urine flow >0.5 ml/kg/hr using furosemide, normal saline bolus and ionotropes as necessary. The use of nonsteroidal anti-inflammatory drugs and other nephrotoxic agents such as aminoglycosides will be avoided if possible, which is consistent with the standard of care of treating all critically ill children. The use of all medications and fluid boluses will be recorded.

e. Protocol for electrolyte imbalance

Metabolic derangements such as hypernatremia, hypokalemia, hypocalcemia or severe alkalosis will be treated as per standard of care in the PICU. Severe alkalemia, defined as $\text{pH} > 7.6$, can be associated with ventricular arrhythmias and seizures. Therefore, any subject with serum $\text{pH} > 7.55$ will have the intervention fluids immediately discontinued. As per standard of care, electrolytes will be rechecked after any treatment intervention. Adverse events such as hypernatremia, hypokalemia and severe alkalosis will be monitored.

f. Follow up Visit

Subjects will be seen in the outpatient cardiothoracic clinic on Day 30, as is done routinely. Each subject will have height, weight, comprehensive metabolic panel and complete blood count measured as part of the research protocol.

g. Pilot study to test dose of Sodium Bicarbonate

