To ensure that the chosen dose of sodium bicarbonate adequately alkalinizes the urine, we will briefly halt enrollment to blindly review urine pHs of the first 10 randomized subjects. The research nurse will be blinded to the patients' enrollment arm and the information regarding the results of the urine pH will not be available to the investigators until this interim analysis to assure appropriate blinding during the treatment of each patient. Since we have blocked randomization in groups of 10, we expect that half of the subjects will receive treatment with Sodium Bicarbonate. Therefore, we expect half of the subjects to have urine pH close to 7. If we find that urine is not adequately alkalinized, we will halt the study and submit a modification to the IRB to alter the dose of sodium bicarbonate.

VI. Study Outcomes

Demographic and Clinical Data

The medical record will be abstracted for the following variables: age, gender, diagnosis, previous surgical history, race, left ventricular ejection fraction on baseline echo, and current medications. Surgical parameters of cardio-pulmonary bypass time, ischemic time, surgical procedure, surgical complexity score, lowest temperature, use of circulatory arrest, use of cerebral perfusion, renal NIRS (measure of oxygen saturation of the renal vessels), medications administered, pH range, urine pH, surgical time, post-bypass time, estimated blood loss, and blood products administered will be measured. Cumulative fluid balance (daily Ins and Outs), hospital and intensive care unit length of stay, need for and duration of dialysis and medical complications will be recorded.

Serum NGAL is a biomarker of early AKI that often increases before serum creatinine. Specifically for this research study, serum NGAL and creatinine level will be drawn at the time of surgery and at 2, 4, 12, 24, and 48 hours.

As per routine care, creatinine will then be measured daily. pRIFLE level will be calculated on the maximum creatinine attained.

| pRIFLE Criteria | | |
|------------------------|---|---|
| | GFR | Urine Output |
| Risk | decrease by 25% | 0.5 mL/kg/h for 8 hours |
| Injury | decrease by 50% | 0.5 mL/kg/h for 16hours |
| Failure | decrease by 75% or GFR <35 | 0.3 mL/kg/h for 24 hours or anuric for 12 hours |
| Loss | Persistent failure 4 weeks | |
| End stage | End-stage renal disease (persistent failure 3 mo) | |

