Creatinine clearance will be estimated by the Schwartz formula ($k \times ht \text{ (cm)} / \text{creatinine}$; $k = 0.4$ premature, $k = 0.55$ females and pre-pubertal males <13 , $k = 0.7$ pubertal males). NGAL will be measured by enzyme-linked immunosorbent assay. Urine pH will be measured at 2, 4, 12, 24 hours post surgery, and as described above, the investigators will be blinded to these results. Serum pH and electrolytes will be measured at 2, 4, 12, 24 hours. NGAL and urine pH will be measured specifically for the purpose of performing this research study. Serum pH is routinely measured as standard practice in post-operative cardiothoracic surgery patients during surgery, and at hours 2, 12, and 24 hours post-operatively.

PART E. Statistical Issues

I. Statistical Analysis

Statistical analyses will be done using SPSS 18.0 (SPSS Inc., Chicago, IL) statistical package. A two-tailed p-value < 0.05 is the criterion for statistical significance. Intention to treat analysis will be done. Descriptive statistics will be used to characterize outcome measures in subjects. Means, standard deviations, 95% confidence intervals, medians, and minimum and maximum values will be tabulated and reported for all continuous variables. Frequency counts and percentages will be used for categorical variables. The distributions of each outcome will be examined for normality. Baseline demographic and clinical data of the two arms will be examined. Differences in means in the treatment group will be compared to the control group using Student’s t-test, or the Wilcoxon Rank Sum test if the data are not normally distributed. Differences in proportions will be assessed using the chi-square test.

Specific Aims:

1. To analyze the primary outcome, chi-square will be conducted to compare the proportion of subjects who develop AKI by pRIFLE criteria in the two groups.

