We will monitor for clinical adverse events throughout the study. We will promptly report all unanticipated problems related to research to the IRB. Refer to DSMB section for specifics. Participation in all areas of the study is completely voluntary. Should the subjects become intolerant of any aspect of the study, their participation (or the specific procedure) will be discontinued. Subjects in severe cardiogenic shock post-operative requiring extra-corporeal membrane oxygenation (ECMO) or left ventricular assist device (LVAD) will be withdrawn from the study. Study investigators will be responsible for communicating to subjects' information arising from the study (on harm or benefit), or from other research on the same topic, that could affect subjects' willingness to continue the study. All other aspects of the study will be kept confidential. Data will be stored in a locked cabinet and password protected file.

c. Potential Benefits to Subjects and Others

One group might receive more effective treatment and/or have fewer side effects than the other treatment groups. This study has considerable future potential benefit for all children with cardiac surgery in preventing AKI.

d. Data Collection and Management

The Investigators are responsible for data management and accuracy of records. Data will be kept in a secure location in an office in the PICU. Each patient will have a separate folder with all data collected within. All data will be entered into a database by an investigator or study coordinator with unique identifiers attached to each patient. Data will be encrypted and password protected.

e. Confidentiality

All data and records generated during this study will be kept confidential in accordance with Institutional policies and HIPAA on subject privacy and that the Investigator and other site personnel will not use such data and records for any purpose other than conducting the study.

In order to keep protected health information from disclosure, subjects will be assigned unique identifiers known only to IRB approved study personnel..

Storing Documents in Hard Copy

If you are storing documents in hard copy:

Any documents that contain subjects' PHI (e.g., consent forms) will be stored in a locked cabinet within the office of study investigator's in the PICU, separately from any de-identified research data. IRB approved personnel will be the only individuals with access to the research data.

Storing Documents Electronically

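### Children who need ECMO or LVAD are withdrawn from the study after randomisation, and this rule is not reconciled with the promised intention-to-treat analysis

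*Combined protocol and SAP*

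**What the plan says.** **The withdrawal rule.** It stands in Part D, section III, directly below the exclusion criteria: children in severe cardiogenic shock after surgery "requiring extra-corporeal membrane oxygenation (ECMO) or left ventricular assist device (LVAD) will be withdrawn from the study". Part F (Protection Against Risk) repeats it, ending "left ventricular assist device (LVAD) will be withdrawn from the study".

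**Its timing.** Part D, section V.b fixes the order of events on the day of surgery: "Subjects will then be randomized into one of the treatment groups and will receive the intervention at the start of surgery". A post-operative need for ECMO or LVAD therefore comes after randomisation and after exposure.

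**The analysis rule.** Part E, section I has one sentence: "Intention to treat analysis will be done". The primary test is a chi-square on the proportion with AKI. Part D, section VI bases the pRIFLE level on the highest creatinine reached.

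**What is not said.** No section says whether withdrawn children stay in the denominator, whether their outcomes are still collected, or how AKI status is assigned if it is missing.

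**What would be available anyway.** Apart from items marked as research and some 4-hour blood draws, section V says "All other procedures represent standard practice for all patients undergoing cardiopulmonary bypass". After the 48-hour sampling series, section VI says "As per routine care, creatinine will then be measured daily". Dialysis and length of stay are also abstracted from the medical record.

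**The concern.** Three readings of the withdrawal sentence are open:

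- **Dropped:** the child leaves the AKI comparison.
- **Truncated:** the child stays in the denominator but is classified only on data up to withdrawal.
- **Followed:** study participation ends, but the child is analysed as randomised from routine records.

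Only the third fits intention to treat, and no sentence states it. The protocol's wording elsewhere adds doubt. Where only the fluid stops, section V.e says that subjects "will have the intervention fluids immediately discontinued". Withdrawal from the study is a broader phrase.

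Under the first two readings, the primary comparison is conditioned on, or cut short by, an event after randomisation. A link between that event and AKI is plausible, but this is clinical reasoning and is not in the documents. The secondary outcomes of dialysis, progression to pRIFLE F, ventilation and length of stay are exposed in the same way, because severe values may be concentrated in the sickest children.

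**Working it through.** **1. The plan's own figure.** Part E, section II gives 66 per arm for 50% against 25% AKI, two-sided alpha 0.05, power 80%.
- Uncorrected: n = [1.960·√(2·0.375·0.625) + 0.842·√(0.5·0.5 + 0.25·0.75)]² / 0.25² = 57.7, so 58.
- Continuity-corrected: (57.7/4)·[1 + √(1 + 4/(57.7·0.25))]² = 65.4, so 66. The stated figure reproduces.
- Enrolment is 132 = 2 × 66, so there is no allowance for withdrawal. Corrected power is 80.4% with all children kept. It is 79.5% if 2% are dropped and 78.0% if 5% are dropped.

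**2. Assumptions.** The documents give neither an ECMO/LVAD rate nor the AKI risk in such children. Assume a withdrawal rate w of 2% to 5%: 66 × 0.02 = 1.3 and 66 × 0.05 = 3.3, or about 1 to 3 children per arm. Let r be the AKI risk in withdrawn children and m the share of their cases missed. True AKI is 50% in both arms (no effect).
- Dropped: AKI risk among those retained = (0.5 − w·r)/(1 − w). At w = 5%, r = 1 this is 0.45/0.95 = 47.4%; at w = 2% it is 0.48/0.98 = 49.0%.
- Truncated: observed risk = 0.5 − w·r·m. At w = 5%, r = m = 1 this is 45%; at w = 2% it is 48%.

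**3. Type I error.** Exact enumeration, Pearson chi-square without continuity correction, every withdrawn child with AKI (r = 1):

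| Withdrawn, bicarbonate / control | Dropped | Kept, every case missed |
|---|---|---|
| nobody | 4.5% | 4.5% |
| 2% / 2% | 4.9% | 4.5% |
| 5% / 5% | 5.1% | 4.6% |
| 5% / 2% | 5.4% | 5.8% |

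With r = 75%, the last row becomes 5.1% and 5.25%. With continuity correction, dropping gives 3.5% at 5%/2%, against 3.2% to 3.3% for equal withdrawal.

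**4. Timing.** Section V.c reports that "85% of patients who develop AKI do so in the first 24 hours". A child already classified as AKI before withdrawal is not lost to a binary endpoint. If withdrawal came at 24 hours with typical timing, 15% of cases would be missed, and the 5%/2% figure for truncation falls from 5.8% to 4.5%.

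**5. Direction.** When dropped at 5%/2%, the 5.38% splits into 3.78% favouring bicarbonate and 1.61% favouring control. At 2%/5% the split reverses.

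**6. The estimate under the design effect.** Equal withdrawal is not neutral here. Dropping 5% per arm, all with AKI, gives (0.50 − 0.05)/0.95 = 47.4% against (0.25 − 0.05)/0.95 = 21.1%. The risk ratio is 0.44 instead of 0.50, and the risk difference 26.3 points instead of 25.0.

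**7. Borderline results** (control against bicarbonate, uncorrected p). From 33/66 v 21/66 (p = 0.034), losing three control cases gives 0.067, and losing three bicarbonate cases gives 0.013. From 33/66 v 22/66 (p = 0.052), losing one bicarbonate case gives 0.040. The continuity-corrected values for that last pair are 0.077 and 0.060, so it does not cross 0.05. On average, removing one bicarbonate case moves the uncorrected result across 0.05 in 1.1% of trials with no effect and in 2.5% at 50% v 25%.

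**The case against.** The strongest reply is that Part E already settles the matter. Intention to treat is the only analysis-set rule in the documents, and in its ordinary meaning it keeps every randomised child in the assigned arm. The withdrawal sentences sit under eligibility and risk protection and mention neither denominators nor the test. Part F also distinguishes ending participation from ending a specific procedure, so the wording stays open.

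Much of this stands. A reader might infer that the plan has no intention-to-treat commitment, or that it orders these children out of the analysis. The documents support neither: the commitment is explicit, and no sentence prescribes exclusion. But intention to treat decides how a child is counted. It cannot supply outcomes that are no longer collected, and leaving the study, read literally, stops that collection.

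A reader might also infer a serious inflation of type I error. Figures of 8.1% (dropped) and 14.4% (kept, every case missed) can be produced, but they need withdrawal of 10% against 2% and AKI in every withdrawn child. Nothing in the documents supports such an imbalance. They give no sign that the fluid affects ECMO or LVAD use, and treatment is blinded (Part D, section IV).

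**Conclusion.** The point holds as a conflict between two stated rules that the documents do not reconcile. Confidence is high that the reconciling sentence is missing, and lower about what follows from that.

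Within the assumed 2% to 5% range, the worst cases are 5.4% against 4.9% to 5.1% (dropped) and 5.8% against 4.5% (kept, every case missed). The direction depends on which arm loses more children and is unknown. That the effect is small is itself conditional on low ECMO/LVAD rates, which the documents do not give. A result near 0.05 could turn on a few children. Severity is minor to moderate: the likely impact is modest, but the remedy is nearly free and is best settled before any outcome comparison by arm.

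**What to change.** - **Part D, section III and Part F (Protection Against Risk):** separate any decision about study fluid from leaving the study. The fluid decision is a clinical matter and is not judged here. State that children who need ECMO or LVAD stay in outcome collection from routine records, including the daily creatinines, unless consent is withdrawn. Say whether the scheduled samples up to 48 hours continue or only routine results are used.
- **Part E, section I:** state that the intention-to-treat set includes these children as randomised, with the AKI definition unchanged, and say how AKI is assigned if it is missing.
- **Reporting:** give ECMO/LVAD counts by arm. Exclude these children only in a sensitivity analysis.

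The cost is a few sentences and one table row. No additional blood draws are needed if routine results are used, and the planned 66 per arm is preserved. The one drawback is that creatinine and urine output may be noisier during support; the sensitivity analysis would show whether this matters.

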Dose: Subjects in the intervention arm will receive NaHCO₃ as a continuous infusion of D5% 1/3NS + 100 meq/L NaHCO₃ + 20 meq/L KCl at maintenance IVF (1500 ml/m²/day). The solution contains ~154 meq of sodium which is equivalent to normal saline. The strength of NaHCO₃ is based on a dose of 150 meq/m²/day. Per Lexicomp, the dose for prevention of hyperuricemia secondary to tumor lysis syndrome (urinary alkalization) in infants and children is sodium bicarbonate IV 120-200 mEq/m²/day diluted in I.V. fluids of 3000 mL/m²/day. 3000 ml/m²/day is two times normal maintenance IVF. Given that this protocol is for cardiac patients, there is a risk of fluid overload with two times maintenance IVF. Therefore, we have chosen a lower dose of sodium bicarbonate 150 meq/m²/day to be diluted in one times maintenance IVF (1500 ml/m²/day). The study drug will be obtained from the CCMC pharmacy. This dosing regimen will be tested in the first 10 subjects, see Section V.g.

Dosage Forms: Injection, solution: 4.2% [5 mEq/10 mL] (10 mL); 8.4% [10 mEq/10 mL] (50 mL) Neut®: 4% [2.4 mEq/5 mL] (5 mL) [contains edetate disodium] 1 mEq NaHCO₃ is equivalent to 84 mg; each g of NaHCO₃

provides 12 mEq each of sodium and bicarbonate ions; the osmolarity of 0.5 mEq/mL is 1000 mOsm/L and 1 mEq/mL is 2000 mOsm/L

Monitoring Parameters: Serum electrolytes including calcium, urinary pH, arterial blood gases

Pharmacodynamics: Onset of action: I.V.: Rapid Duration: I.V.: 8-10 minutes

Pharmacokinetics: Elimination: Reabsorbed by kidney and <1% is excreted in urine

PART D. Experimental Design and Methods

I. Overview of Study Design

A prospective, randomized, double-blinded, placebo-controlled trial in children undergoing cardiac surgery with cardio-pulmonary bypass will be conducted to determine the effect of sodium bicarbonate on the prevention of acute kidney injury. A total of 132 subjects will be enrolled (66 subjects in each arm) at a single pediatric tertiary hospital, Cohen Children's Medical Center of New York, over a two year time period.

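### A fixed block size of 10, stated in the protocol, combined with unmasked serum chemistry leaves an avoidable risk that some allocations near the end of a block can be predicted

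*Combined protocol and SAP*

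**What the plan says.** All references are to the combined protocol and SAP.

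- **Allocation (Part D.IV).** "Subjects will be randomized to the treatment group or control group in a 1:1 ratio". The method follows: "Allocation will be based on random, computer-generated numbers in permuted blocks of 10". No other size is given, and nothing says that the size is kept from the investigators.
- **Use of the block size (Part D.V.g).** The dose check on the first ten subjects relies on it: "Since we have blocked randomization in groups of 10, we expect that half of the subjects will receive treatment with Sodium Bicarbonate".
- **Setting (Part D.I).** "A total of 132 subjects will be enrolled (66 subjects in each arm) at a single pediatric tertiary hospital".
- **Blinding (Part D.IV).** "The investigators involved in the study, clinicians and study subjects will be blinded to the treatment assignment", and "Study drug and placebo will be prepared and dispensed by the pharmacy according to randomization".
- **Timing (Part D.V.b).** After baseline tests on the day of surgery, "Subjects will then be randomized into one of the treatment groups and will receive the intervention at the start of surgery". The procedures table puts consent earlier, at screening.
- **What is masked.** V.d and VI withhold urine pH results from the investigators, and V.d gives protection of the blind as the reason.
- **What is not masked.** Under VI, "Serum pH and electrolytes will be measured at 2, 4, 12, 24 hours", and serum pH is described as routine care. V.b and V.c have the anaesthesiologist act on intra-operative electrolytes. V.e ties stopping of the study fluid to a serum pH limit, so the treating team must see that result.

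**The concern.** Blinding is meant to stop anyone learning which arm earlier children received. Here the plan itself treats pH as a possible route to unblinding, because it masks urine pH, yet serum chemistry stays visible. Part C says the drug raises blood pH as well as urinary pH. The two bags also differ in composition. The treatment fluid contains 100 mEq/L of bicarbonate and, taking normal saline as 154 mEq/L, about 154/3 + 20 = 71 mEq/L of chloride. The control fluid contains 154 + 20 = 174 mEq/L of chloride and no bicarbonate.

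If earlier arms can be guessed, a known block of 10 with five in each arm turns those guesses into information about the next allocation. The choice of which family to approach, or when, could then depend on the expected arm. Such selection happens before randomisation, so blinding of later care does not undo it. The primary analysis in Part E is an unadjusted chi-square test, which does not undo it either.

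**Working it through.** The plan gives no figure for predictability, so there is none to reproduce.

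**Inputs.** Block size 10 and ratio 1:1 (Part D.IV); 132 subjects at one site (Part D.I). 132 = 13 × 10 + 2, that is, 13 full blocks and two children over. The accuracy *q* with which an observer recognises each earlier child's arm is an assumption, because the documents give nothing from which to estimate it.

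**Step 1: certain allocations, all earlier arms known (q = 1).** An allocation is certain once one arm has used its five places.

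| Position | Calculation | Probability certain |
|---|---|---|
| 1st–5th | | 0 |
| 6th | 2/252 | 0.8% |
| 7th | 10/210 | 4.8% |
| 8th | 20/120 | 16.7% |
| 9th | 20/45 | 44.4% |
| 10th | | 100% |

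The sum is 1.67 per block, which equals 2m/(m + 1) = 10/6 with m = 5. The 9th and 10th supply 1.44 of the 1.67. Over 13 blocks: 13 × 1.67 = 21.7 children, or 21.7/132 = 16.4%.

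**Step 2: best-guess rate, q = 1.** The observer guesses the arm that is behind in the block. Expected correct guesses per block are m + (4^m / C(2m, m) − 1)/2 = 5 + (1024/252 − 1)/2 = 6.53, or 65.3%, against 50% by chance.

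**Step 3: imperfect recognition.** 100,000 simulated blocks, guessing against the apparent majority within the block:

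| Assumed q | Overall guess rate | 10th child |
|---|---|---|
| 1.0 | 65.3% | 100% |
| 0.9 | 59.2% | 70.5% |
| 0.8 | 55.9% | 60.8% |
| 0.7 | 53.7% | 56.1% |
| 0.6 | 51.8% | 53.2% |

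**Step 4: what varying the size would achieve.** The comparison is with an observer who knows the set of sizes but not the block boundaries, and who uses all the information.

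- *q = 1, certain allocations.* Random 8/10/12 throughout gives about 1.3%. With the first block kept at 10: (1.67 + 0.013 × 122)/132 = (1.67 + 1.59)/132 = 2.5%, so about 2%, against 16.4%. If the observer also counts down to a known 66:66 close, the last child is certain too: (1.67 + 1.59 + 1)/132 = 3.2%.
- *q = 1, guess rate.* 65% for 8/10/12 against 65% for fixed 10.
- *q = 0.9, predictions held with at least 80% confidence.* About 2% with fixed 10, and about 0.2% with varying sizes and the first block kept. The retained block alone gives 1.9% × 10/132 = 0.14%.
- *q = 0.9, guess rate.* About 59% with fixed 10, and about 58% with sizes centred on or above 10.
- *Smaller sizes, 4 to 10.* The guess rate is 67% against 65% at q = 1, and about 59% and 56% at q = 0.9 and 0.8, the same as for fixed 10.

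**The case against.** The strongest reply is that recognition may be poor. V.c gives controls bicarbonate too, through the pump prime and base-deficit correction. V.b allows boluses in either arm and has electrolyte abnormalities treated. The 71 v 174 mEq/L contrast describes the bags, not the blood. Urine pH, the direct marker, is masked after surgery. At 70% recognition even the 10th child is guessed correctly only 56% of the time. This stands: the size of the risk is unknown.

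The chance to act on a guess is also limited. Consecutive eligible patients are invited (Part D.III), data are recorded on ineligible and declining children (V.a), and the pharmacy dispenses (D.IV). Consent comes before randomisation on the day of surgery, so an enroller would also have to foresee the order of operations. These safeguards reduce the risk but do not remove it, because the approach to the family still comes before allocation. A block of 10 is also less predictable than a fixed 4 or 6 (65% against 71% and 68% with all earlier arms known).

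A reader might infer more than the documents support:

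- *That the whole team knows each child's place in the block, or that those who approach families also schedule cases and read the chemistry.* No section says so.
- *That there is one unstratified list.* This is a natural reading of silence plus a single site, but it is not stated, and the argument does not need it.
- *That varying the size lowers the guess rate, say from 59% to 54% at 90% recognition or from 56% to 52% at 80%.* Those gaps appear only if the guesser counts within blocks for the fixed design and over the whole list for the varying one. Counting over the whole list with fixed blocks of 10 also gives 54% and 52%.

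**Conclusion.** The concern holds as an avoidable risk of partial predictability. It does not show that the randomisation is broken. The fixed size, its disclosure and the open serum results are all in the documents. With perfect recognition, about 22 of 132 allocations would be certain and the guess rate would be 65%. At 90%, 80% and 70% recognition the rate is about 59%, 56% and 54%. All these recognition levels are assumptions.

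A reader might conclude that later allocations in each block can simply be predicted. That goes too far. Certainty requires the earlier arms in the block to be identified correctly, and it falls mainly on the last two places. Nor does the urine pH review in V.g itself help to predict later blocks, since it covers one complete block.

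The benefit of varying the size is the removal of nearly all certain and near-certain predictions, with the average guess rate about the same or slightly lower. This is a low-severity design improvement, worth making because it costs so little.

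**What to change.** In Part D.IV:

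1. Keep the first block at 10, because V.g relies on it.
2. Generate the rest of the list in randomly varying block sizes centred on or above 10, for example 8/10/12, or 6 to 14. Avoid 4 to 10, which does not lower the guess rate and raises it slightly if all earlier arms are known.
3. Let the last block close the list at 66:66. Thirteen blocks of 10 plus two children do not guarantee that split.
4. State that block sizes and order are held only by the pharmacy or list generator, and replace the fixed-size wording with: *permuted blocks of varying size, not disclosed to investigators*. Limit the V.g statement to the first ten subjects.

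The cost is a new computer-generated list before enrolment, a sentence or two of protocol text, and slightly looser balance between arms at interim points. Sample size and analysis do not change.
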